Treatment Protocol	Neuromodulation Group: Multimodal neuromodulation targeting specific neural regions in addition to conventional therapy. Control Group: Sham stimulation in addition to conventional therapy.
Efficacy Assessment	Primary Outcome Measures: Fugl-Meyer Assessment score; neuroimaging data (cranial CT/MRI); EEG measurements of resting-state and task-state spectral power and functional connectivity; laboratory parameters (complete blood count, CRP, IL-6, S100 β , BDNF). Secondary Outcome Measures: Brunnstrom staging, Modified Ashworth Scale grading, muscle strength, and patient comfort assessment. Safety Assessment Indicators: Complete blood count, blood biochemistry, coagulation function.
Statistical Methods	Key outcome measures will be compared between the neuromodulation group and the control group before and after intervention using independent samples t-tests (two groups) or analysis of variance (multiple groups) to detect statistically significant intergroup differences. Non-parametric tests will be applied to data not conforming to a normal distribution.
Study Duration	March 2026 – March 2028

1. Background and Rationale

According to the World Health Organization (WHO), stroke is the second leading cause of death globally [1]. Approximately 15 million individuals worldwide experience a stroke annually, ranking second only to heart disease, and stroke remains one of the most prevalent causes of long-term disability. Ischemic stroke (IS) constitutes the most common subtype, accounting for approximately 85% of all stroke cases [2]. Among all stroke survivors, over 60% experience varying degrees of functional impairment within three months following the event. The American Stroke Association (ASA) has reported [3] that approximately one-third of stroke patients develop severe speech impairment post-stroke, while one in two patients sustains some degree of hand function loss. Stroke patients frequently contend with chronic functional deficits, including motor difficulties, speech impairment, and cognitive dysfunction, all of which profoundly compromise quality of life. These patients typically require prolonged rehabilitation and nursing care, imposing substantial financial burden on families and exerting considerable pressure on healthcare systems.

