3.2 Sample Size

Participants will be recruited from inpatients of the Department of Rehabilitation Medicine. Based on preliminary literature review and the current inpatient volume of our department, the provisional sample size is set at $n = 60$, with 30 participants allocated to each group.

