3.4 Participant Selection

Inclusion Criteria: (1) Patients with a confirmed imaging diagnosis of first-ever ischemic stroke; (2) Unilateral limb motor involvement; (3) Modified Ashworth Scale (MAS) grade ≤ 3 for the upper extremity, Brunnstrom stage II–V, and upper extremity Fugl-Meyer Assessment (FMA-UE) score between 15 and 60 (inclusive); (4) Age 18–75 years, onset within 21 days

to 6 months, in the subacute or recovery phase; (5) Stable vital signs, no consciousness impairment, informed consent provided, ability to cooperate with clinical assessments, and approval obtained from the institutional ethics committee.

Exclusion Criteria: (1) Contraindications to MRI; (2) Infarction involving the thalamus; (3) Risk of intracranial hemorrhage; (4) Presence of intracranial metallic foreign bodies, cardiac pacemakers, or cochlear implants; (5) Unstable medical condition, severe cognitive impairment or psychiatric disorders rendering the patient unable to comprehend the study or cooperate with assessments; (6) Conditions affecting limb motor function, including fractures, joint contractures, or severe limb spasticity; (7) Current use of medications that alter cortical excitability.

Withdrawal Criteria: (1) Health risks: Occurrence of serious health events such as acute cardiovascular events or other severe illnesses; (2) Non-compliance: Failure to adhere to the treatment protocol or follow-up requirements, compromising data reliability; (3) Personal reasons: Voluntary withdrawal from the study due to personal circumstances; (4) Severe adverse reactions: Occurrence of unmanageable treatment-related discomfort, such as extreme pain or allergic reactions.

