3.5.4 Screening Phase

Medical history documentation will be collected, including sex, age, medical record number, history of present illness, and past medical history. The following examinations will be completed: blood biochemistry, complete blood count, coagulation function, and neuroimaging (cranial CT/MRI). Baseline clinical assessments will be performed, including the Fugl-Meyer Assessment, Brunnstrom staging, and Modified Ashworth Scale grading.

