3.8 Efficacy Assessment

Primary Outcome Measures: Post-treatment (immediate and 2-week follow-up) upper extremity Fugl-Meyer Assessment score, Brunnstrom staging, and Modified Ashworth Scale grading; neuroimaging data (analysis of ALFF, fALFF, ReHo, FC, and FA indices using functional MRI and diffusion tensor imaging); EEG measurements of resting-state and task-state spectral power and functional connectivity.

Secondary Outcome Measures: Blood biochemistry, complete blood count, C-reactive protein (CRP), interleukin-6 (IL-6), S100 β protein, and brain-derived neurotrophic factor (BDNF).

4. Risks and Benefits

4.1 Potential Risks and Mitigation Measures: Abnormal reactions to ultrasound stimulation and potential induction of seizures. Adverse symptoms such as dizziness and headache will be promptly managed. Short-term administration of analgesic agents and antiepileptic medications will be employed as indicated.

4.2 Potential Benefits and Compensation for Participants:

Direct Benefits: Promotion of hemiplegic upper limb functional recovery and enhancement of activities of daily living capacity.

Societal Benefits: It is anticipated that information obtained from this study may benefit the participant or future patients with similar conditions.

5. Adverse Event Monitoring

5.1 Adverse Events (AEs): An adverse event is defined as any unfavorable medical occurrence, unanticipated illness or injury, or unexpected clinical sign (including abnormal laboratory findings) in a participant or other individual, regardless of whether it is considered related to the study intervention or treatment strategy under investigation.

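### The only stated between-group test uses no baseline adjustment and leaves open whether scores or changes are compared; adjusting for baseline FMA-UE would gain precision at no cost

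*Protocol*

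**What the plan says.** The protocol describes its statistical methods in one place, the Statistical Methods row of the Synopsis. Key outcomes are to be "compared between the neuromodulation group and the control group before and after intervention using independent samples t-tests (two groups"), with analysis of variance if there are more groups. The fallback is: "Non-parametric tests will be applied to data not conforming to a normal distribution". Neither sentence names a covariate, a change score or a repeated-measures model.

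The other relevant statements are:

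- Section 3.4 admits patients with an "upper extremity Fugl-Meyer Assessment (FMA-UE) score between 15 and 60 (inclusive").
- Section 3.5.4: "Baseline clinical assessments will be performed, including the Fugl-Meyer Assessment, Brunnstrom staging, and Modified Ashworth Scale grading".
- Section 3.6 describes a one-week course of pre-test, stimulation and post-test, and lists clinical scales in the pre-test.
- Section 3.8 lists as a primary outcome the "Post-treatment (immediate and 2-week follow-up) upper extremity Fugl-Meyer Assessment score".
- Section 3.2 sets the size at 60, "with 30 participants allocated to each group". Section 3.5.5 allocates by random number table, with no stratification stated.

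**The concern.** The stated method can be read in two ways.

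On the plain reading, the arms are tested twice, once at baseline and once after treatment. The baseline test answers no question: under randomisation any baseline difference is due to chance. The post-treatment test then leaves out the one measurement most likely to explain differences between patients. Entry scores may span 45 points, and the first outcome comes about a week after baseline, so much of the spread after treatment may simply be the spread at entry.

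On the other reading, the t-test is on change from baseline. Baseline is then used, though not in the most efficient way.

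The protocol should not leave this choice open. With 60 patients, and a size that rests on a literature review and inpatient volume, the efficiency of the analysis is one of the few things that can still be improved without recruiting more people.

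**Working it through.** **No figure to reproduce.** Section 3.2 gives 60 patients without alpha, power, effect size or SD, so there is no power claim to check. The steps below compare analyses at the stated 30 per arm.

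**Inputs from the protocol.** 30 per arm; entry FMA-UE 15 to 60; baseline FMA collected; outcomes immediately after treatment and at 2 weeks.

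**Assumptions, not in the protocol.** Two-sided 0.05; 80% power; no dropout; equal SD before and after treatment; r from 0.5 to 0.9; SD 13, with a range of 8 to 15. The value 13 is what an even spread over the entry range would give: 45/√12 = 13.0.

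**Step 1: variance of the estimated treatment difference.** With n per arm and outcome SD σ:

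- post-treatment score only: 2σ²/n, taken as 1
- change score: 2(1 − r) relative to that
- adjusted for baseline (ANCOVA): 1 − r² relative to that

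The post-only test therefore gives up a fraction r² of the attainable precision. The change-score variance exceeds that of ANCOVA by 2/(1 + r) − 1.

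| r | ANCOVA variance | Precision given up, post-only | Change-score variance | Excess of change over ANCOVA |
|---|---|---|---|---|
| 0.5 | 0.75 | 25% | 1.00 | 33% |
| 0.7 | 0.51 | 49% | 0.60 | 18% |
| 0.8 | 0.36 | 64% | 0.40 | 11% |
| 0.9 | 0.19 | 81% | 0.20 | 5% |

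**Step 2: detectable difference.** With 30 per arm the standardised difference detectable at 80% power is 0.736 (noncentral t, 58 df). The normal approximation gives 0.723. At SD 13 the post-only test detects 0.736 × 13 = 9.6 points (9.4 by the normal approximation). The other designs multiply this by the square root of the relative variance:

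| r | Post-only | Change score | ANCOVA |
|---|---|---|---|
| 0.5 | 9.6 | 9.6 | 8.3 |
| 0.7 | 9.6 | 7.4 | 6.8 |
| 0.8 | 9.6 | 6.0 | 5.7 |
| 0.9 | 9.6 | 4.3 | 4.2 |

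The one degree of freedom spent on the covariate is ignored; its effect is small.

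**Step 3: dependence on the SD.** All entries in step 2 scale with the SD. The post-only figure is 0.736 × 8 = 5.9 points at SD 8 and 0.736 × 15 = 11.0 at SD 15. The ratios between the columns do not change.

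**Step 4: check by simulation.** For an illustrative 5-point difference at SD 13, with 4,000 runs at each r, power was:

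| r | Post-only | Change score | ANCOVA |
|---|---|---|---|
| 0.5 | 30% | 32% | 39% |
| 0.7 | 31% | 47% | 52% |
| 0.8 | 30% | 63% | 67% |
| 0.9 | 31% | 90% | 91% |

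This agrees with the formulas. The 5 points serve only to compare the methods.

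**The case against.** **The text may mean change scores.** If so, baseline is not discarded, and at r = 0.8 to 0.9 the standard error is only about 3% to 5% above that of ANCOVA (√1.053 to √1.111). This objection stands as far as it goes: the Synopsis wording allows that reading. Section 3.8, however, names a post-treatment score, and the Synopsis reads most naturally as two separate between-group comparisons. Either way the text needs the same clarification.

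**The size rests on assumptions.** This also stands. A reader might infer that the plan gives up most of its precision. That needs r² above one half, so r above 0.71, and the protocol gives no correlation. A high r is plausible over one to three weeks with so wide an entry range. At r = 0.71 and SD 13, individual changes would have an SD of about 13 × √(2 × 0.29) = 9.9 points, so a lower r would need even more variable change. Plausible is not documented, however, and at r = 0.5 the loss is a quarter.

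**The unadjusted test is valid.** Correct. A reader might infer that a chance baseline imbalance biases the result. At SD 13 the standard error of the baseline difference is 13 × √(2/30) = 3.4 points, so a gap above 5 points would occur in about 14% of such trials; at SD 8 it would be about 1.5%. Such imbalance is already part of the unadjusted standard error. Over repeated randomisation the test is unbiased and keeps its type I error.

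**A separate SAP may settle this.** It may, and the lack of a covariate would not by itself be a finding. The point is that the protocol does name a test, and a better one is available from data already being collected.

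The clause on several groups is harmless in a two-arm trial. The non-parametric fallback is a minor matter and does not carry the argument.

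**Conclusion.** The point holds as one of efficiency and clarity. The only stated analysis is an unadjusted two-sample test whose response variable is not identified. If post-treatment scores are compared, as Section 3.8 suggests, the loss against a baseline-adjusted analysis is r²: from 25% to 81% of the precision over the assumed range of r. If changes are compared, the loss is modest: a variance 5% to 33% above that of ANCOVA. The percentages depend on r and on equal SDs before and after treatment; the differences in points also depend on the assumed SD. The documents do not show that the trial's result would be biased, that its type I error would be wrong, or that most of its precision is certain to be lost. The between-group baseline tests should go on any reading.

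**What to change.** Replace the Statistical Methods row, for FMA-UE, with a statement to this effect:

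- FMA-UE is analysed by a linear model of the post-treatment score on arm and baseline FMA-UE, at one named time point (immediate or 2 weeks). If both times are used, a mixed model with visit and visit-by-arm terms takes its place.
- The result is reported as the adjusted mean difference with a 95% confidence interval.
- The arms are described at baseline but not tested against each other.

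The text should also say which assessment is the baseline, since Section 3.5.4 places one at screening and Section 3.6 lists clinical scales in the pre-test.

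The cost is wording in the Synopsis and in any SAP. No new visits, measurements or patients are needed. The version is dated April 2026 and Section 8 plans allocation from June 2026, so on the protocol's own timetable the change could be fixed before the first patient is randomised.

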3.1 Study Design

This study is a randomized, controlled, single-center trial.

3.2 Sample Size

Participants will be recruited from inpatients of the Department of Rehabilitation Medicine. Based on preliminary literature review and the current inpatient volume of our department, the provisional sample size is set at $n = 60$, with 30 participants allocated to each group.

3.3 Study Duration

March 2026 – March 2028

3.4 Participant Selection

Inclusion Criteria: (1) Patients with a confirmed imaging diagnosis of first-ever ischemic stroke; (2) Unilateral limb motor involvement; (3) Modified Ashworth Scale (MAS) grade ≤ 3 for the upper extremity, Brunnstrom stage II–V, and upper extremity Fugl-Meyer Assessment (FMA-UE) score between 15 and 60 (inclusive); (4) Age 18–75 years, onset within 21 days

to 6 months, in the subacute or recovery phase; (5) Stable vital signs, no consciousness impairment, informed consent provided, ability to cooperate with clinical assessments, and approval obtained from the institutional ethics committee.

Exclusion Criteria: (1) Contraindications to MRI; (2) Infarction involving the thalamus; (3) Risk of intracranial hemorrhage; (4) Presence of intracranial metallic foreign bodies, cardiac pacemakers, or cochlear implants; (5) Unstable medical condition, severe cognitive impairment or psychiatric disorders rendering the patient unable to comprehend the study or cooperate with assessments; (6) Conditions affecting limb motor function, including fractures, joint contractures, or severe limb spasticity; (7) Current use of medications that alter cortical excitability.

Withdrawal Criteria: (1) Health risks: Occurrence of serious health events such as acute cardiovascular events or other severe illnesses; (2) Non-compliance: Failure to adhere to the treatment protocol or follow-up requirements, compromising data reliability; (3) Personal reasons: Voluntary withdrawal from the study due to personal circumstances; (4) Severe adverse reactions: Occurrence of unmanageable treatment-related discomfort, such as extreme pain or allergic reactions.

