Five neuromodulation sessions are administered in total. Sessions 2 and 5 involve simultaneous EEG-coupled ultrasound neuromodulation, while Sessions 1, 3, and 4 consist of ultrasound neuromodulation alone. During EEG-coupled sessions, EEG signals are acquired before, during, and after ultrasound stimulation; during standalone sessions, only ultrasound stimulation is delivered without EEG acquisition. Stimulation parameters are maintained at consistent control levels across participants. Based on each individual's

cranial acoustic parameters, the pre-attenuation stimulation intensity is back-calculated to ensure uniform in situ intensity at the target. The spatial-peak temporal-average intensity at the target is maintained below the diagnostic ultrasound safety threshold (720 mW/cm²). The ultrasound stimulation duration is 12 minutes using a 20% duty cycle pulse sequence.

The post-test cranial MRI protocol is identical to the pre-test and is performed within two days of completion of all neuromodulation sessions.

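### The withdrawal criteria do not separate stopping stimulation from leaving the study, so non-adherent patients can be lost after randomisation and the comparison can be biased

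*Protocol*

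**What the plan says.** The withdrawal criteria in Protocol section 3.4 have four items: (1) serious acute illness; (2) non-compliance, worded "Failure to adhere to the treatment protocol or follow-up requirements, compromising data reliability"; (3) personal reasons, worded "Voluntary withdrawal from the study due to personal circumstances"; and (4) severe adverse reactions, worded "Occurrence of unmanageable treatment-related discomfort, such as extreme pain or allergic reactions". There is no separate list of reasons for stopping stimulation.

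Other sections bear on how the list works:

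- Section 3.1: "This study is a randomized, controlled, single-center trial".
- Section 3.2: 60 participants, "with 30 participants allocated to each group".
- Section 3.6: "Five neuromodulation sessions are administered in total", once daily within one week.
- Section 3.7: sham participants go through the same preparation with the ultrasound left off. Participants are the only people stated to be blinded.
- Section 3.8: the upper-extremity Fugl-Meyer score (FMA-UE) is assessed immediately after treatment and at 2 weeks.

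No section says that a withdrawn participant still has these assessments.

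**The concern.** Adherence and tolerance are observed after allocation and may depend on both the arm and the prognosis. If patients leave on those grounds, the groups that remain are no longer the groups that were randomised.

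Three features of the text make this a practical risk. First, item (3) speaks of withdrawal from the study, so the natural reading is that the whole list governs leaving the study and not only ending stimulation. Second, item (2) gives no threshold, such as a number of missed sessions. Whether someone is non-compliant is a judgement, and the staff who make it are not stated to be blinded. Third, item (2) also covers follow-up requirements. On its wording, a patient who completes all five sessions and the immediate FMA-UE but misses the 2-week visit could be withdrawn.

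What is at stake is the validity of the between-arm FMA-UE comparison and, secondarily, some of the precision of a 60-patient trial.

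**Working it through.** **The plan's own figures.** There is no withdrawal figure to reproduce. Section 3.2 rests the sample size on "Based on preliminary literature review and the current inpatient volume of our department" and states no effect size, SD, significance level, power or dropout rate. The only input below that comes from the protocol is 30 per arm. Everything else is an assumption used to show scale.

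**Illustration in FMA-UE points.** Suppose m of 30 active patients are removed and none in sham, and the removed patients gained δ points less than the rest of their arm. If the rest average M, the mean of the full arm is

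[(30 − m)M + m(M − δ)] / 30 = M − δ × m/30.

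Analysing only those who remain therefore overstates the active mean by δ × m/30.

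| δ (assumed) | m = 3 | m = 5 |
|---|---|---|
| 5 points | 5 × 3/30 = 0.50 | 5 × 5/30 = 0.83 |
| 8 points | 8 × 3/30 = 0.80 | 8 × 5/30 = 1.33 |

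With an assumed SD of change of 5, the standard error of the difference is 5 × √(2/30) = 1.29. The overstatement is then roughly 0.4 to 1.0 standard errors (0.50/1.29 = 0.39; 1.33/1.29 = 1.03).

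**Withdrawals in both arms, no true effect.** Let qA and qC be the shares withdrawn in the active and sham arms, and let g be the gap in SD between those who stay and those who leave, the same in both arms. The shift in the difference is g × (qA − qC). The two-sided type I error comes from the normal approximation with SE = √(1/nA + 1/nC) and nominal 5%.

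| Withdrawn, active vs sham | Shift for g = 0.25 to 1.0 SD | Type I error |
|---|---|---|
| 10% vs 5% | 0.013 to 0.05 SD | 5.0% to 5.4% |
| 10% vs 0% | 0.025 to 0.10 SD | 5.1% to 6.6% |
| 20% vs 5% | 0.04 to 0.15 SD | 5.2% to 8.4% |
| 20% vs 0% | 0.05 to 0.20 SD | 5.4% to 11.3% |
| 20% vs 20% | 0 | 5.0% |

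The two calculations agree where they overlap: 10% vs 0% with g = 1.0 SD is a shift of 0.10 × 5 = 0.50 points, the first cell of the first table.

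**Precision.** At an assumed two-sided 5% level, 30 per arm gives 80% power for 0.72 SD. Losing 10% per arm lowers this to 76%, and losing 20% per arm to 71%.

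**The case against.** The strongest reply is that the text is being read too harshly and that the harm is not shown. Much of this stands.

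- **Certain bias, or an effect that must be overstated.** A reader might infer this, but the documents give neither withdrawal rates nor any way to know how the withdrawn patients would differ. At 10% versus 5% withdrawn the type I error barely moves, and with matching shares and patients there is no bias. Five sessions in inpatients may keep the numbers low.
- **A nearly intact sham arm.** Reactions caused by the ultrasound itself can arise only in the active arm, since sham leaves it off (sections 3.7 and 4.1). But items (1) to (3) apply to both arms, and sham patients have the same positioning and coupling gel. An allergic reaction, which item (4) names, could come from the gel.
- **Any missed session leads to removal, or collected data are deleted.** The clause about data reliability can be read as limiting item (2) to serious non-adherence. The protocol nowhere says that data already collected are discarded.
- **Safety follow-up ends at withdrawal.** Sections 5.1 and 5.2 define adverse events and set no such end point.
- **A larger illustration.** Dividing by the patients who remain (5 × 3/27 = 0.56; 5 × 5/25 = 1.0) fits only a gap measured against the full-arm mean. For a gap against the rest of the arm, the divisor is 30.
- **Analysis sets belong to the statistical analysis plan.** That is fair, and their absence from the protocol is not the complaint.

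What the reply does not remove is the rule itself. A statistical analysis plan, which was not available here, can define who is analysed. It cannot recover outcomes that were not collected because the protocol had withdrawn the patient.

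**Conclusion.** The point holds as a defect in stated protocol text. Section 3.4 makes non-adherence and treatment-related reactions grounds for withdrawal without separating the end of stimulation from the end of participation, and nothing elsewhere keeps these patients under assessment. The rule can bias the randomised comparison. The documents do not support saying that it will, by how much, or in which direction.

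On the assumed values (removals in the active arm only, 3 to 5 of 30, removed patients gaining 5 to 8 points less than the rest), the active mean is overstated by 0.50 to 1.33 FMA-UE points against a standard error of about 1.3. That scenario is one-sided by construction. More balanced withdrawal gives a smaller shift, down to zero. The change should be made because it is cheap and lost outcomes cannot be recovered later, not because a large error has been demonstrated.

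**What to change.** Reword the withdrawal criteria in section 3.4 as follows.

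1. Keep the clinical reasons for stopping stimulation exactly as written, and state that stopping stimulation is not the same as leaving the study.
2. Delete non-compliance as a reason for removal from the study. Record it as adherence data instead.
3. Continue the immediate and 2-week FMA-UE and adverse event recording in every participant who still consents and can be assessed. This need not commit a patient with acute illness to the full post-test, which includes MRI.
4. Compare participants in their assigned arm, with any adherence-based analysis as sensitivity only. This can be placed in the statistical analysis plan, provided the protocol secures the data for it.

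The cost is a protocol amendment with ethics approval under section 6.1, a few extra assessments, and possibly a slightly smaller estimate. Section 8 plans allocation from June 2026, so the wording is best settled before then, or as early as possible if allocation has begun.
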